7.2.2 Visit Attendance

The number and percentage of participants who attended a visit or received a safety call within the interval described in Table 3 and per the naming conventions in Table 8 will be presented for the following visits:

- Visit 1 Day 1
- Telephone Contact 1 Day 8
- Visit 2 Day 22
- Telephone Contact 2 Day 29
- Visit 3 Day 43
- Telephone Contact 3 Month 4
- Telephone Contact 4 Month 7
- Telephone Contact 5 Month 10
- Telephone Contact 6 Month 13

The number and percentage of participants with attendance at each study visit will be summarized by study group, age group, and overall for the Exposed Set. Listings will be provided for the Exposed Set to provide details of visit attendance, safety calls, and blood samples.

An additional table with the number and percentage of participants with a deviation from the study and with the minimum and maximum days deviated will be generated by treatment group and overall.

The deviation intervals included in this table for the PPSx and MNPPSx will be:

- Between 18 – 25 days from Visit 1 to Visit 2
- Between 38 – 46 days from Visit 2 to Visit 3

The deviation intervals included in this table for the mPPSx and mMNPPSx will be:

- Between 18 – 32 days from Visit 1 to Visit 2
- Between 14 – 32 days from Visit 2 to Visit 3

A table with all deviations from intervals according to [Table 3](#) will be added in the final analysis.

8 Immunogenicity Analysis

The primary immunogenicity objective of this study is to evaluate whether the vaccine with monovalent H7N9 virus containing 1.9 μ g, 3.75 μ g, or 7.5 μ g of HA adjuvanted with AS03_A or AS03_B elicits a HI antibody response to the vaccine-homologous virus that meets or exceeds the US FDA, CBER immunogenicity criteria at the Day 43 visit. Section 4.3 defines the conditions under which the observed immune responses will meet the guidelines.

The secondary immunogenicity objectives of this study are to describe the vaccine homologous H7N9 HI and MN antibody profiles at Days 1, 22, and 43.

The primary and secondary H7N9 HI immunogenicity analyses will be based on the applicable PPSx as described in section 4.6. Supplementary analyses for primary and secondary HI immunogenicity analyses will be based on the applicable mPPSx. Results for baseline values will be presented using PPS2 and mPPS2 accordingly. If the difference between PPS 1 and FAS 1 is greater than 10%, a second analysis based on the applicable FASx will be performed to complement the PPSx analysis.

The H7N9 MN immunogenicity analyses will be based on the applicable MNPPSx as described in section 4.6. Supplementary analyses for MN immunogenicity analyses will be based on the applicable MN mPPSx.

For a given participant and a given immunogenicity measurement, missing or non-evaluable measurements will not be replaced.

Titers below cut-off will be handled as described in Section 4.5.

H7N9 HI titer results will be listed for the Exposed Set and the listing will indicate participants included in each of PPSx, mPPSx and FASx. The listing will also indicate participants with HI titers \geq cut-off and participants who experienced a 4-fold increase in HI titers since baseline. A similar listing will also be prepared for the H7N9 MN titer results for the MN Set and the listing will indicate participants included in each of MNPPSx and MNmPPSx.

For the remainder of Section 8 the Analysis Visit names defined in Table 8 will be used.

The primary and secondary immunogenicity analyses will be presented in the same outputs.

8.1 Seroconversion Rate (SCR) and Seroprotection Rate (SPR)

The percentage of participants with seroconversion (SCR) and seroprotection (SPR) will be calculated along with Clopper-Pearson exact two-sided CIs by intervention group, age group, and post-baseline visit. For Day 43 only, the CIs will be 99.17% for the antigen/adjuvant groups and will allow testing of the statistical hypotheses. For Day 1 (SPR only) and Day 22 (SCR and SPR) and Placebo (including Day 43), the CIs will be 95% and are provided for descriptive purposes only.

The SCR and SPR will be analyzed for H7N9 HI antibody titer only.

8.2 Geometric Mean Titer

Titer results are not normally distributed so summary statistics will be calculated using log-transformed titer results. The anti-logarithm of the summary statistics will be presented. Titer results will be summarized by study group, age group, visit. Missing titer results and results below the cut-off will be handled as described in Section 4.5.

In addition, the distribution of antibody titers for each intervention group and age group will be displayed using reverse cumulative distribution curves. The x-axis of the reverse cumulative distribution curves will be presented on a log scale. A reference line will be included to show the cut-off. All study groups for a single visit will be displayed on the same page, and visits will be displayed on separate pages.

Summaries will include the number of participants with non-missing titer results, GMT, geometric standard deviation (GSD), 95% CI for GMT, minimum and maximum.

GMT will be calculated as the anti-logarithm of the mean of the log-transformed titer values i.e. anti-logarithm of $\sum(\log_{10}(titer))/n$ where n is the number of participants with non-missing titer results. GSD will be calculated as the anti-logarithm of the standard deviation (SD) of the log-transformed data. The 95% CI for GMT will be calculated as the anti-logarithm of the endpoints of the 95% CI for the mean of the log-transformed data. The anti-logarithm is calculated as 10^x where x is the statistic of interest calculated from the log-transformed data (e.g. mean, SD, 95% CI endpoints).

No adjustment will be made for multiplicity in GMT and CIs are provided for descriptive purposes only. The GMT will be analyzed for both H7N9 HI and MN antibody titers.

8.3 Mean Geometric Increases (MGIs)

MGI for HI will be summarized by study group, age group, and post-baseline visit. Missing titer results and results below the cut-off will be handled as described in Section 4.5.

MGI will be calculated as the anti-logarithm of the mean of the change from baseline of log-transformed titer values at Post-Baseline and Baseline i.e. anti-logarithm of $\sum(\log_{10}(titer_{Post-Baseline\ AVISIT}) - \log_{10}(titer_{Baseline}))/n$ where n is the number of participants with non-missing titer results at Baseline and Post-Baseline AVISIT.

Summaries will include the number of participants with non-missing titer results at each post-baseline AVISIT, MGI, GSD of the difference in log-transformed titer results at post-baseline AVISIT and Baseline, 95% CI for MGI, minimum and maximum.

GSD will be calculated as the anti-logarithm of the SD of the change from baseline of the log-transformed data. The 95% CI for MGI will be calculated as the anti-logarithm of the endpoints of the 95% CI for the mean MGI. The anti-logarithm is calculated as 10^x where x is the statistic of interest calculated from the log-transformed data (e.g. mean, SD, 95% CI endpoints).

No adjustment will be made for multiplicity in MGI and CIs are provided for descriptive purposes only. The MGI will be analyzed for H7N9 HI antibody titers only.

8.4 Seropositivity

The percentage of seropositive participants for HI and MN as well as the associated Clopper-Pearson exact 2-sided 95% CIs will be computed by study group, age group and visit.

No adjustment will be made for multiplicity in seropositivity and CIs are provided for descriptive purposes only. Seropositivity will be analyzed for both H7N9 HI and MN antibody titers.

8.4.1 Vaccine Response Rate (VRR)

The VRR for MN as well as the associated Clopper-Pearson exact 2-sided 95% CIs will be computed by study group, age group and post-baseline visit.

No adjustment will be made for multiplicity in VRR and CIs are provided for descriptive purposes only. The VRR will be analyzed for H7N9 MN antibody titers only.

9 Safety Analysis

Safety summaries and listings will be based on the Exposed Set.

9.1 Adverse Events

Solicited events, unsolicited AEs, SAEs, medically attended AEs, AEs leading to withdrawal from intervention or from the study, and pIMDs that occur post-vaccination will be summarized and also presented in listings. AEs occurring prior to a participant receiving any study vaccine will be listed only.

The definitions for SAEs and medically attended AEs can be found in protocol sections 10.3.2 and 10.3.9.3 respectively. Further information about pIMDs can be found in protocol section 10.3.5.1.

Incomplete onset dates and end dates for any AEs will be imputed to determine if the event occurred within the time period specified for AE summaries that are described in sections 0 and 9.1.2. Actual dates recorded will be presented in listings, imputed dates will not be presented. Incomplete dates will be imputed as follows:

Missing onset dates (where UK and UKN indicate unknown or missing day and month respectively):

- If the response to “If exact start date is unknown, or is on the same day as any study vaccination, please confirm whether it occurred before or after vaccination:” is “After vaccination 1” or “After vaccination 2” then assume the start date is the date of the first and second dose of study vaccine, respectively.
- If the response is “Before vaccination” assume the following:
 - UK-MMM-YYYY: If the month and year are different from the month and year of the first dose of study vaccine, assume 01-MMM-YYYY. If the month and year are the same as the first dose of study vaccine month and year, and the end date (after any imputation) is on or after the first dose of study vaccine, then assume the date of the first dose of study vaccine. If the month and year are the same as the first dose of study vaccine month, and year and the end date (after any imputation) is prior to the first dose of study vaccine, then assume the end date for the onset date.
 - DD-UKN-YYYY/UK-UKN-YYYY: If the year is before the year of first dose of study vaccine, assume DD-JAN-YYYY/01-JAN-YYYY of the collected year. If the year is after the first dose and the same as the second dose, assume DD-JAN-YYYY/01-JAN-YYYY. If the year is the same as the first dose of study vaccine year, and the end date (after any imputation) is on or after the first dose of study vaccine, then assume the date of the first dose of study vaccine. If the year is the same as the first dose of study vaccine, and the end date (after any imputation) is prior to the first dose of study vaccine, then assume the end date for the onset date.

Missing end dates (where UK and UKN indicate unknown or missing day and month respectively):

- UK-MMM-YYYY: Assume the last day of the month.
- DD-UKN-YYYY: Assume DD-DEC-YYYY.
- UK-UKN-YYYY: Assume 31-DEC-YYYY.

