9.4.3.2. Safety

The analysis of reactogenicity and unsolicited events will be based on the ES.

Solicited administration site and systemic endpoints

- Occurrence of each solicited administration site events during a 7-day follow-up period (Day 1 to Day 7) after each vaccination.
- Occurrence of each solicited systemic events during a 7-day follow-up period (Day 1 to Day 7) after each vaccination.

All solicited events will be summarized according to defined severity grading scales.

Frequencies and percentages of participants experiencing each event will be presented for each symptom severity. Summary tables showing the occurrence of any solicited administration site events or solicited systemic events overall and at each time point will

also be presented and will be tabulated with Clopper-Pearson exact 95% CIs. Solicited administration site events will be assessed according to which vaccine was administered.

If a solicited event occurs more than once for a participant, it will be counted in the summary only once for each level of summarization, according to the maximal severity. Summary tables showing the occurrence of any solicited administration site events or solicited systemic events overall will be presented.

Unsolicited AE endpoints (Amended 22 February 2022)

- Occurrence and relationship to vaccination of unsolicited AEs within 21 days after each vaccination.
- Occurrence and relationship to vaccination of AEs with MAEs within 21 days after each vaccination.

SAE endpoints

- Occurrence and relationship to vaccination of SAEs and pIMDs up to Day 43 visit.
- Occurrence and relationship to vaccination of SAEs and pIMDs until Month 13.

This analysis applies to all AEs, whether judged either as probably related, possibly related, or not related to vaccination by the investigator, recorded in the Adverse Events eCRF, with a start date on or after the date of first vaccination and not later than 21 days of the most recent vaccination. Adverse events starting prior to the first vaccination will only be listed. The original verbatim terms used by investigators to identify AEs in the eCRFs will be mapped to preferred terms using the Medical Dictionary for Regulatory Activities. The AEs will then be grouped by Medical Dictionary for Regulatory Activities preferred terms into frequency tables according to system organ class.

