The informed consent of the participant must be signed before study participation. All inclusion and exclusion criteria will be checked as described in Protocol Sections 5.1 and 5.2 before dosing on Day 1.

On Visit 1 (Day 1) informed consent will be obtained and pre-vaccination procedures will be carried out. Upon satisfactory completion of pre-vaccination 1 procedures, participants will be randomized to a study group and intervention number and will have blood samples drawn before receiving the first dose of study vaccine.

Participants will be observed closely for at least 30 minutes following the administration of the vaccine, with appropriate medical treatment readily available in case of anaphylaxis and/or syncope.

Participants will have a second dose of study vaccine/product administered at Visit 2 following satisfactory completion of pre-vaccination 2 procedures. Participants will have blood drawn at Visit 1 pre-vaccination, Visit 2 pre-vaccination and Visit 3 to test for immune response.

An unsolicited AE is an AE that was not solicited using a Participant Diary and that was spontaneously communicated by a participant who has signed the informed consent. Unsolicited AEs include serious and non-serious AEs. Unsolicited AEs will be recorded for 21 days following administration of study vaccine/product. AEs will be recorded starting from informed consent date.

Serious adverse events (SAEs), medically attended AEs (MAEs), AEs/SAEs leading to withdrawal, SAEs related to study participation or concurrent GSK medication/vaccines and potential immune mediated diseases (pIMDs) will be recorded from the date of informed consent through Month 13. The pIMDs are listed in Protocol Table 19.

Solicited events include administration site and systemic events and are solicited using a Participant Diary. Solicited administration site events include pain, redness, and swelling. Solicited systemic events include fatigue, fever, gastrointestinal (nausea, vomiting, diarrhea, abdominal pain), headache, muscle ache, joint pain, shivering (chills), and sweating.

Participants will receive a safety follow-up call after each visit where study vaccine/product is administered. Solicited events will be recorded in participant diaries by the participant for 7 days after the vaccine/product is administered (including the day on which the vaccine/product is administered). For solicited events continuing after 7 days, the participant will be instructed to record events

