9.1.2 Unsolicited Adverse Events

An unsolicited AE is an AE that was not solicited using a participant Diary and that was spontaneously communicated by the participants or a solicited administration site or systemic event that meets the criteria described in Section 0. Solicited events lasting more than 7 days after vaccination (including the day of vaccination) are also recorded as unsolicited AEs.

The original verbatim terms used by investigators to identify AEs in the Adverse Events page of the eCRF will be mapped to preferred terms (PT) using MedDRA, version to be delineated in the CSR. The AEs will then be grouped by MedDRA according to system organ class (SOC).

The following summaries will present the event count, number and percentage of participants reporting each AE and will be presented by SOC, PT, and maximum relationship to study intervention for each study group, grouped by 21 days post-vaccination at any visit and then by 2 time points (at the final analysis): 21 days post-vaccination at Visit 1, and 21 days post-vaccination at Visit 2:

- Any unsolicited AE
- Any severe unsolicited AE (grade 3)
- Any related unsolicited AE
- Any severe related unsolicited AE (grade 3 related)
- Unsolicited MAEs
- Any AEs with MAEs
- Any related AEs with MAEs

Additional summaries will present the number and percentage of participants reporting AEs in the following categories and will be presented by SOC and PT for each study group and age group from Day 1 through the Day 43 visit and from Day 1 through the end of study:

- SAEs
- AEs leading to withdrawal from study drug (through Day 22 only)
- AEs leading to withdrawal from study
- MAEs (within 21 days post each vaccination)
- pIMDs

Data listings of all AEs will be provided by participant. In addition, AEs in the categories above will be provided as listed data.

Missing data will be handled as described in Section 4.5.

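### SAP 9.1 sets an incomplete AE onset marked as after a dose to that dose date even when the recorded month or year rules it out, which can bring a late event into the 21-day tables

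*SAP*

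**What the plan says.** SAP 9.1 states the purpose of the imputation: "Incomplete onset dates and end dates for any AEs will be imputed to determine if the event occurred within the time period specified". The imputed onset therefore decides which table an event enters.

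Where the site answers *After vaccination 1* or *After vaccination 2*, the instruction is to "then assume the start date is the date of the first and second dose of study vaccine, respectively". The branch for *Before vaccination* works differently and reads the recorded parts. For a known month: "If the month and year are different from the month and year of the first dose of study vaccine, assume 01-MMM-YYYY". For a known year it has a separate rule, which begins "DD-UKN-YYYY/UK-UKN-YYYY: If the year is before the year of first dose of study vaccine".

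On collection, SAP 3.1 says that "Unsolicited AEs include serious and non-serious AEs" and that SAEs, MAEs, AEs leading to withdrawal and "potential immune mediated diseases (pIMDs) will be recorded from the date of informed consent through Month 13". For MAEs this differs from the schedule of activities and SAP 10.4, which stop MAE collection after the 21-day periods.

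On selection, Protocol 9.4.3.2 takes AEs that start on or after the first vaccination and "not later than 21 days of the most recent vaccination". SAP 9.1.2 begins its 21-day tables with any unsolicited AE and splits them by dose at the final analysis. SAP 4.5 assigns AEs to periods by the start date recorded in the eCRF and gives no rule for a partial date.

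**The concern.** The dose date is a sensible default when nothing about the onset is known. It is not sensible when the site has recorded a month or year that cannot contain the dose date. The SAP ignores that information in the branch that feeds the post-vaccination tables, and uses it in the branch whose events are mostly only listed.

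Unsolicited AEs and MAEs within 21 days of each vaccination are a primary safety endpoint. A serious event from, say, five months after dose 2 could be tabulated as starting on the day of vaccination. The listing would show the recorded month but not the imputed date, so table and listing would disagree with no displayed reason.

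**Working it through.** **Inputs.** Dose 2 on Day 22 and Visit 3 on Day 43 (allowed to Day 46); Month 13 contact allowed to Day 395; dose 2 allowed on Days 18–25 (SAP Table 3). The 21-day period is the day of vaccination plus the next 20 days (Protocol 10.3.8). Study groups of 120, age-by-group cells of 60 (SAP Table 2).

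**The plan's own figure.** The imputation rule has none. The nearest is Protocol Table 15 (exact 95% CI, N = 60). For 0/60 the upper limit is 1 − 0.025^(1/60) = 6.0%; for 1/60 the interval is 0.0% to 8.9%. Both agree with the table.

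**When does the recorded month alone rule out the window?** Let the dose date be d and the window end d + w. The month is incompatible if its first day falls after d + w. For the calendar month after the dose month, this holds for L − w dose dates in a dose month of L days. A 365-day year has seven months of 31 days, four of 30 and one of 28.

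- 21-day window, w = 20: 7 × 11 + 4 × 10 + 8 = 125 of 365.
- Day 43, w = 21: 7 × 10 + 4 × 9 + 7 = 113 of 365. The same count applies to the 21-day window if the Protocol 9.4.3.2 limit is read as dose date + 21.
- Visit 3 on Day 46, w = 24: 7 × 7 + 4 × 6 + 4 = 77 of 365.
- Two or more calendar months later: the shortest gap is 29 days (31 January to 1 March), longer than any of these windows, so 365 of 365.
- Same month as the dose: 0 of 365. Here the SAP rule is harmless.

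**Worked dates.** Dose 2 on 10-Mar-2022; 21-day window ends 30-Mar; Day 43 is 31-Mar. The SAP rule gives 10-Mar-2022 in every row.

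| Recorded onset | Earliest compatible date | Study day | In 21-day window? |
|---|---|---|---|
| UK-MAR-2022 | 10-Mar-2022 | 22 | yes |
| UK-APR-2022 | 01-Apr-2022 | 44 | no |
| UK-AUG-2022 | 01-Aug-2022 | 166 | no |
| 15-UKN-2022 | 15-Mar-2022 | 27 | yes |
| 05-UKN-2022 | 05-Apr-2022 | 48 | no |
| UK-UKN-2023 | 01-Jan-2023 | 319 | no |

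The largest possible shift is 395 − 22 = 373 days after dose 2, or 395 − 1 = 394 days with dose 1 only.

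**After vaccination 1.** Taking this to mean between the doses in participants who receive dose 2, the days outside the 21-day window are 0 of 21 with dose 2 on Day 22 and 3 of 24 with dose 2 on Day 25. In that last case the recorded month excludes the window in 72 of 365 × 24 = 8760 combinations of dose date and onset day (0.8%). The exposure is therefore after dose 2, or in participants who never receive it.

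**Effect of one misplaced participant.** 1/60 = 1.7 points in an age-by-group cell (0%, upper limit 6.0, becomes 1.7%, upper limit 8.9). 1/120 = 0.8 points in a study group (upper limit 3.0 becomes 4.6).

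**The case against.** The strongest objection is that the path from the rule to a wrong table runs through eCRF pages that the documents do not show. SAP 4.5 names separate pages for non-serious and for serious/expedited events. Nothing shows that the latter accepts partial dates or carries the before/after question. The Protocol's AE analysis and SAP 9.1.2 speak of the Adverse Events eCRF without saying whether that includes the expedited page. This stands, and it makes the consequence conditional. SAP 9.1 does cover any AE and unsolicited AEs include serious ones, so the path is plausible, but it is not established.

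SAP 4.5 also points to recorded start dates. It is silent on partial dates, so it does not override SAP 9.1.

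Third, the effect is probably small. SAEs are reported within 24 hours of awareness and events are followed to resolution, so month-only onsets should be uncommon. Safety is descriptive, and the rule is the same in every arm. All of this stands. That the dose date is cautious is only partly true: a misplaced placebo event would narrow the contrast with vaccine.

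A reader might infer that the Day 43 report or the Month 13 SAE and pIMD totals would be wrong. The documents do not support that. The Day 43 report uses data only through that visit, and the totals to end of study do not depend on where in the period an onset falls. The Day 1 to Day 43 SAE/pIMD tables would be affected only if rerun at Month 13. That is implied by SAP 10.3, which covers all primary endpoints, but not stated.

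**Conclusion.** The rule is wrong as written: it can assign an onset date that the recorded month or year contradicts. Its consequence is conditional. It requires that partial dates and the before/after answer are available for events collected beyond 21 days: SAEs, pIMDs, AEs leading to withdrawal and, on SAP 3.1 alone, MAEs. If so, a late event, mainly after dose 2 or after dose 1 only, would be counted in the 21-day unsolicited AE/MAE tables at the final analysis.

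The number of such events is not given and is probably small. When one occurs with a recorded month at least two calendar months after the dose 2 month, the misplacement is certain; in the next month it is demonstrable for 125 of 365 dose dates. These counts assume dose 2 on Day 22 and no particular onset distribution. The recorded date in the listing lets a reader find such an event, but only by comparing it with the table.

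**What to change.** For *After vaccination 1* or *After vaccination 2*, impute the earliest date on or after that dose that is compatible with the recorded parts:

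- UK-MMM-YYYY: the dose date if month and year are those of the dose; 01-MMM-YYYY if the month is later.
- UK-UKN-YYYY: the later of the dose date and 01-JAN-YYYY.
- DD-UKN-YYYY: the first day DD in the recorded year on or after the dose.
- No parts recorded: the dose date.
- No compatible date on or after the dose, for example a month or year before it: query the site.

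Cross-refer SAP 4.5 to this rule, so that period assignment uses the recorded date when complete and the imputed date otherwise. It would also help to state whether the Day 1 to Day 43 SAE/pIMD tables are rerun at Month 13.

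The cost is a few lines of SAP text and of date-derivation code. Data collection does not change.

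### SAP 9.1 can date an adverse event that the site reported as starting before vaccination to the day of dose 1, so that it counts as a post-vaccination event

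*SAP*

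**What the plan says.** SAP 9.1 completes partial AE dates so that each event can be placed inside or outside a summary period. Where the start date is unknown, the eCRF asks whether the event began before or after vaccination. The SAP has branches for three answers: 'After vaccination 1', 'After vaccination 2' and 'Before vaccination'. The last one works as follows.

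- **Day unknown, month known.** "If the month and year are different from the month and year of the first dose of study vaccine, assume 01-MMM-YYYY". If month and year match dose 1 and the end date, after imputation, "is on or after the first dose of study vaccine, then assume the date of the first dose of study vaccine". If the end date is earlier than dose 1, the onset is set to the end date.
- **Month unknown.** "If the year is before the year of first dose of study vaccine, assume DD-JAN-YYYY/01-JAN-YYYY of the collected year". When the recorded year is that of dose 1, the same end-date test applies, and an event that meets it is again given the first-dose date, even if a day of the month was recorded.
- **End dates** are completed late: "UK-MMM-YYYY: Assume the last day of the month", and December when the month is missing.

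On events before dosing, SAP 9.1 says "AEs occurring prior to a participant receiving any study vaccine will be listed only" and Protocol 9.4.3.2 says "Adverse events starting prior to the first vaccination will only be listed". Protocol 9.4.3.2 defines the AE analysis by start date: the day of first vaccination or later, up to 21 days after the most recent dose. SAP 4.5 also assigns unsolicited AEs to periods by start date and time.

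**The concern.** Dating an event to the dose is a sensible cautious choice when nobody knows whether it began before or after the injection. Here the site has been asked and has answered. The rule sets an onset that no longer reflects that answer, and the date criterion then admits the event to the tables from which the same section excludes it.

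Unsolicited AEs, medically attended AEs, SAEs and potential immune-mediated diseases are all primary safety endpoints, and onset on the day of vaccination is the timing most suggestive of a vaccine effect. The misplacement would also be hard to trace. SAP 9.1 keeps imputed dates out of the listings, so a table would count a Day 1 event while the listing showed only a partial date.

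**Working it through.** The plan gives no figure to reproduce, so the check applies the SAP 9.1 rules literally to test cases.

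**Inputs.** Assumed for illustration: dose 1 on 15 March 2021, dose 2 on 5 April 2021, answer 'Before vaccination' in every case. From SAP 4.2: study day = date − dose 1 date + 1 on or after dose 1, and date − dose 1 date before it. From Protocol 9.4.3.2: an event is analysed if its start date is on or after dose 1 and within 21 days of the most recent dose.

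| Case | Recorded onset | Recorded end | Imputed onset | Study day | Result |
|---|---|---|---|---|---|
| A | UK-MAR-2021 | 20 Mar 2021 | 15 Mar 2021 | 15 − 15 + 1 = 1 | in tables |
| B | UK-FEB-2021 | 20 Mar 2021 | 1 Feb 2021 | −42 | listed only |
| C | UK-MAR-2021 | 10 Mar 2021 | 10 Mar 2021 | 10 − 15 = −5 | listed only |
| D | UK-MAR-2021 | UK-MAR-2021, set to 31 Mar | 15 Mar 2021 | 1 | in tables |
| E | 10-UKN-2021 | 20 Mar 2021 | 15 Mar 2021 | 1 | in tables |
| F | UK-UKN-2021 | 20 Mar 2021 | 15 Mar 2021 | 1 | in tables |
| G | UK-UKN-2020 | 20 Mar 2021 | 1 Jan 2020 | −439 | listed only |
| H | UK-MAR-2021 | ongoing, no end date | no rule given | – | undefined |

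**Reading the results.**

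1. A, D, E and F reach Day 1 despite the site's answer.
2. A and B were both ongoing at dosing. They differ only in whether the recorded month is the month of dose 1.
3. In D the event may have ended before 15 March. Moving the end date to 31 March is what brings it in.
4. In E a recorded day is discarded. Any 10th of a month that fits the site's answer is before 15 March, yet the onset becomes 15 March.
5. H has no rule, because the branch tests an end date that does not exist.

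**Size per event.** At the planned numbers, one extra participant with an event adds 1/60 = 1.7 percentage points to an arm-by-age cell, or 1/120 = 0.8 percentage points to an arm. Both are upper bounds at those numbers: percentages count participants, so a row changes only if the participant had no other event in it.

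**Effect of the fix.** If the answer takes precedence, A, D, E and F become listed only, H is resolved, and B, C and G do not change.

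**The case against.** Four arguments on the other side have force.

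- **Few such events should exist.** SAP 3.1 records AEs from consent, and consent and dose 1 are both scheduled at Visit 1. Protocol 10.3.1.2 sends conditions present before the first vaccination to medical history. A reader might infer that long-standing conditions with vague onset would fill the AE tables; the protocol does not support that. SAEs are reported within 24 hours, and autoimmune disorders are an exclusion criterion, so these categories are unlikely sources. This stands and limits the size.
- **Table entry is inferred.** No sentence says that these events are tabulated. The eCRF question also covers events on the day of any vaccination, so a programmer could combine the answer with the listed-only sentence and exclude them. That is possible, but the SAP does not say so, and its stated criterion is the date.
- **Comparisons between arms are little affected.** The rule is the same for placebo, collection is observer-blind, and the safety analysis is descriptive. This stands, and no bias between arms is claimed.
- **For a same-day event the first-dose date may be right.** An event that began at Visit 1 before the injection did start on that calendar day. So the date itself need not be wrong; what is wrong is using it alone to classify the event as post-vaccination.

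A reader might also infer that every 'Before vaccination' event still ongoing at dosing moves to Day 1, or that nearly all do. Neither is supported. Onsets in an earlier month or year stay before the dose (B and G), an event with a known earlier end date stays before it (C), and the documents give no count of partial dates.

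**Conclusion.** The defect is real but narrow. SAP 9.1 contains a stated rule that, read literally, gives the wrong classification to AEs that the site reported as starting before vaccination. It applies only when the known part of the onset date matches dose 1 and the end date after imputation is not before dose 1. The result contradicts the listed-only rule in SAP 9.1 and in Protocol 9.4.3.2, and nothing gives the site's answer precedence.

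The expected effect is small: probably few events, at most 1.7 percentage points each in an arm-by-age cell or 0.8 in an arm, with the same rule in all arms. It is worth correcting mainly for rare categories, where one misplaced event would be noticed, and because the correction is so cheap.

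The conclusion assumes that 'Before vaccination' means before dose 1, which follows from the separate answers for after dose 1 and after dose 2. It also assumes that the tables are built from the imputed date, and that the cells hold the planned 60 and 120 participants.

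**What to change.** Add to SAP 9.1: when the site answers 'Before vaccination' (that is, before dose 1), the answer takes precedence over any imputed onset date, and the event is listed only and excluded from all post-vaccination summaries. Say that this includes events that are ongoing with no end date. Leave the rule for 'After vaccination 1' and 'After vaccination 2' unchanged.

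This is better than capping the onset at the day before dose 1. Consent and dose 1 are scheduled for the same day, so a cap could create an onset before consent.

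The cost is a sentence or two of SAP text and one condition in the AE derivation. No new data are needed, because the eCRF already collects the answer.
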